6.7 Permitted therapies

Including but not limited to hematopoietic growth factors, antimicrobials for prophylaxis or treatment of infections, allopurinol and/or rasburicase for prophylaxis or treatment of TLS.

7 **PRETREATMENT EVALUATION**

- 7.1 A complete history and physical examination including blood pressure, performance status and concomitant medications within 2 weeks prior to start of study treatment.
- 7.2 CBC and differential, albumin, alkaline phosphatase, total, direct and indirect bilirubin, bicarbonate, BUN, calcium, chloride, creatinine, glucose, LDH, phosphorus, potassium, total protein, SGPT (ALT), SGOT (AST), sodium and urinalysis within 1 week prior to start of study treatment.
- 7.3 Serum beta-2-microglobulin and immunoglobulin levels (IgG, IgA, IgM) within 1 week prior to start of study treatment.
- 7.4 Pregnancy test (blood or urine) for female patients of childbearing potential within 7 days (1 week) prior to initiation of study treatment.

- 7.5 Baseline electrocardiogram (ECG) within 1 week prior to start of study treatment.
- 7.6 Baseline bone marrow evaluation and CT scans for assessment of baseline lymphadenopathy and organomegaly are NOT required for study enrollment, but may be performed at any time as needed as standard of care tests.

8 EVALUATION DURING STUDY

- 8.1 Physical examination along with evaluation of performance status, recording of AEs and concomitant medications on day 28 (± 2 days) of each cycle.
- 8.2 CBC and differential on day 28 (± 2 days) of each cycle.
- 8.3 Albumin, alkaline phosphatase, total, direct and indirect bilirubin, bicarbonate, BUN, calcium, chloride, creatinine, glucose, LDH, phosphorus, potassium, total protein, SGPT (ALT), SGOT (AST), and sodium on day 28 (± 2 days) of each cycle.
- 8.4 Serum beta-2-microglobulin and immunoglobulin levels (IgG, IgA, IgM) on day 28 (± 2 days) of each cycle.
- 8.5 ECG on day 28 (± 2 days) of each cycle.
- 8.6 Plasma concentrations of ibrutinib by high performance liquid chromatography with tandem mass spectrometric detection as previously described,⁶⁰ just before dosing and at 4 and 24 hours post-dosing on days 1, 8, and 28 (but before the first dose of the next cycle) of each cycle. Exception: there will be no 4-hour blood draw on day 28. Chemokines will also be measured, using enzyme-linked immunosorbent assay (ELISA).
- 8.7 BTK occupancy level by fluorescent affinity probe detection as previously described,^{9, 60} just before dosing and at 4 and 24 hours post-dosing on days 1, 8, and 28 (but before the first dose of the next cycle) of each cycle. Exception: there will be no 4-hour blood draw on day 28. See section 8.11.
- 8.8 Measurement of BTK mRNA and BTK and phospho-BTK protein and downstream signaling, as previously described,^{74, 75} just before dosing and at 4 and 24 hours post-dosing on days 1, 8, and 28 (but before the first dose of the next cycle) of each cycle. Exception: there will be no 4-hour blood draw on day 28.
- 8.9 Quantification of NF- κ B activation by ELISA as previously described,⁷⁶ just before dosing and at 4 and 24 hours post-dosing on days 1, 8, and 28 (but before the first dose of the next cycle) of each cycle. Exception: there will be no 4-hour blood draw on day 28.
- 8.10 Measurement of platelet functionality as previously described,⁷⁷ just before dosing and at 24 hours post-dosing on days 1 and 28 (but before the first dose of the next cycle) of each cycle.
- 8.11 Peripheral blood samples for plasma ibrutinib and cytokine levels, BTK occupancy, total and phospho-BTK mRNA and protein levels as well as levels of other downstream mediators of BCR signaling, and NF- κ B activity (appendix C) will be sent for processing to the laboratory of [name], Ph.D. at:

[name]
 [name]
 [name]
 [name]
 [contact]
 [contact]
 Email: [contact]

For the BTK occupancy assay, peripheral blood mononuclear cells from blood collected from patients will be isolated in [name] laboratory. The frozen cell pellets then will be transported on dry ice to Pharmacyclics (at the address indicated below). All patient samples are de-identified and neither the hospital number nor the names are included. Laboratories within Pharmacyclics will analyze these samples for the BTK occupancy assay.

Pharmacyclics LLC
 [name]
 [name].

Study Calendar

	Pre- Study	Wk 1	Wk 2	Wk 3	Wk 4	Wk 5	Wk 6	Wk 7	Wk 8	Wk 9	Wk 10	Wk 11	Wk 12
Ibrutinib		A	A	A	A	A	A	A	A	A	A	A	A
Informed consent	X												
Demographics	X												
Medical history	X												
Concurrent meds	X	X-----X											
Physical exam	X				X ^f				X ^f				X ^f
Vital signs	X				X ^f				X ^f				X ^f
Height	X												
Weight	X				X ^f				X ^f				X ^f
Performance status	X				X ^f				X ^f				X ^f

CBC w/diff, plts	X				X ^f				X ^f				X ^f
Serum chemistry ^a	X				X ^f				X ^f				X ^f
Serum beta-2-microglobulin	X				X ^f				X ^f				X ^f
IgG, IgA and IgM levels	X				X ^f				X ^f				X ^f
ECG	X				X ^f				X ^f				X ^f
Adverse event evaluation		X-----X											
β-HCG	X ^b												
Urinalysis	X												
Plasma ibrutinib and chemokine levels		X ^c	X ^d		X ^e	X ^c	X ^d		X ^e	X ^c	X ^d		X ^e
BTK occupancy levels		X ^c	X ^d		X ^e	X ^c	X ^d		X ^e	X ^c	X ^d		X ^e
BTK mRNA, protein and downstream signaling		X ^c	X ^d		X ^e	X ^c	X ^d		X ^e	X ^c	X ^d		X ^e
NF-κB activation assay		X ^c	X ^d		X ^e	X ^c	X ^d		X ^e	X ^c	X ^d		X ^e
Platelet functionality assay		X ^g			X ^g	X ^g			X ^g	X ^g			X ^g

A: Ibrutinib, orally daily, 420 mg/d in cycle 1 (weeks 1-4), 280 mg/d in cycle 2 (weeks 5-8), 140 mg/d in cycle 3 (weeks 9-12).

a: Albumin, alkaline phosphatase, total, direct and indirect bilirubin, bicarbonate, BUN, calcium, chloride, creatinine, glucose, LDH, phosphorus, potassium, total protein, SGOT [AST], SGPT [ALT], sodium.

b: Serum or urine pregnancy test (women of childbearing potential).

c: On day 1 of each cycle, samples at 0 (cycle 1 only), 4, and 24 hours (see appendix C). Please note that the day 1 time zero collection in cycles 2 and 3 coincides with the day 28 24-hour collection of the previous cycles; therefore, no separate day 1 time zero collection is required in cycles 2 and 3.

- d. On day 8 of each cycle, samples at 4 and 24 hours (see appendix C).
- e. On day 28 of each cycle, samples at 24 hours (see appendix C).
- f. On day 28 (± 2 days) of each cycle.
- g. Pre-treatment (cycle 1 day 1) and 24 hours post-dosing on days 1 and 28 of each cycle.

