4.9 Warnings and precautions

Hemorrhage:

Fatal bleeding events have occurred in patients treated with ibrutinib. Grade ≥ 3 bleeding events (subdural hematoma, gastrointestinal bleeding, hematuria and post procedural hemorrhage) have occurred in up to 6% of patients. Bleeding events of any grade, including bruising and petechiae, occurred in approximately half of patients treated with ibrutinib. The mechanism for the bleeding events is not well understood. Ibrutinib may increase the risk of hemorrhage in patients receiving antiplatelet or anticoagulant therapies. Based on the risk-benefit ratio, ibrutinib is suggested to be withheld for at least 3 to 7 days pre- and post-surgery depending upon the type of surgery and the risk of bleeding.

Infections:

Fatal and non-fatal infections have occurred with ibrutinib therapy. Grade ≥ 3 infections occurred in 14% to 26% of patients. Cases of progressive multifocal leukoencephalopathy (PML) have occurred in patients treated with ibrutinib. Patients should be monitored for fever and infections and evaluated promptly.

Cytopenias:

Treatment-emergent Grade 3 or 4 cytopenias including neutropenia (range, 19 to 29%), thrombocytopenia (range, 5 to 17%), and anemia (range, 0 to 9%) occurred in patients treated with ibrutinib. Complete blood counts (CBCs) should be monitored monthly.

Atrial Fibrillation:

Atrial fibrillation and atrial flutter (range, 6 to 9%) have occurred in patients treated with ibrutinib, particularly in patients with cardiac risk factors, acute infections, and a previous history of atrial fibrillation. Patients should be clinically monitored periodically for atrial fibrillation. Patients who develop arrhythmic symptoms (e.g., palpitations, lightheadedness) or new onset dyspnea should have an electrocardiogram (ECG) performed. If atrial fibrillation persists, the risks and benefits of treatment and dose modification should be considered.

Second Primary Malignancies:

Other malignancies (range, 5 to 14%) including non-skin carcinomas (range, 1 to 3%) have occurred in patients treated with ibrutinib. The most frequent second primary malignancy was non-melanoma skin cancer (4 to 11 %).

Tumor Lysis Syndrome (TLS):

TLS has been reported with ibrutinib therapy. Patients should be monitored closely and appropriate precautions taken in patients at risk for TLS (e.g. high tumor burden).

Embryo-Fetal Toxicity:

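### The protocol asks for close tumor lysis monitoring but schedules no chemistry between baseline and day 28 of cycle 1, and never measures uric acid

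*Combined protocol and SAP*

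**What the plan says.** Section 4.9 (Warnings and precautions) notes that TLS has been reported with ibrutinib and continues: "Patients should be monitored closely and appropriate precautions taken in patients at risk for TLS (e.g. high tumor burden". It names no test, analyte or time point.

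The chemistry schedule is set in three places:

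- Section 7.2 (pretreatment) gives a panel ending "LDH, phosphorus, potassium, total protein, SGPT (ALT), SGOT (AST), sodium and urinalysis within 1 week prior to start of study treatment".
- Section 8.3 (during study) gives a panel ending "LDH, phosphorus, potassium, total protein, SGPT (ALT), SGOT (AST), and sodium on day 28 (± 2 days) of each cycle".
- Study Calendar note a lists the serum chemistry analytes, including "bicarbonate, BUN, calcium, chloride, creatinine, glucose, LDH, phosphorus, potassium, total protein, SGOT [AST], SGPT [ALT], sodium". Note f ties the on-treatment panel to day 28 (± 2 days), shown in weeks 4, 8 and 12.

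Potassium, phosphorus, calcium, creatinine and LDH are in all three lists. Uric acid is in none of them.

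Section 6.7 permits, without requiring, "allopurinol and/or rasburicase for prophylaxis or treatment of TLS". Section 5.1.1 requires an ALC of at least 20 × 10⁹/l. On imaging, section 7.6 says: "Baseline bone marrow evaluation and CT scans for assessment of baseline lymphadenopathy and organomegaly are NOT required for study enrollment".

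Blood is nevertheless drawn early in cycle 1. Calendar note c has "On day 1 of each cycle, samples at 0 (cycle 1 only), 4, and 24 hours", and note d has "On day 8 of each cycle, samples at 4 and 24 hours". Section 8.11 and Appendix C send these samples to research assays. No routine chemistry is assigned to them.

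**The concern.** The protocol recognises a risk, asks for close monitoring of it, and then sets a concrete schedule with no matching procedure. A site that follows the schedule exactly gets no chemistry for most of the first month on drug.

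The exposure is narrow but real. Symptomatic TLS would probably prompt tests whatever the calendar says. An asymptomatic biochemical TLS would not, because questioning about adverse events does not reliably reveal it. Section 6.3 requires interruption for grade 3 or higher non-hematologic toxicity, but a silent laboratory abnormality cannot trigger that rule through scheduled tests until the first on-treatment panel. Allopurinol and rasburicase are available under section 6.7, yet the schedule produces no uric acid result to inform their use.

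This is a matter of patient safety. It does not bias the drug level, BTK occupancy or other primary measurements.

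**Working it through.** The plan states no figure on this point to reproduce. The check is a comparison of sections, a day count and a tube count.

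**1. Warnings in 4.9 against the schedule**

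| Warning in 4.9 | Monitoring asked for | Scheduled procedure |
|---|---|---|
| Cytopenias | CBC monthly | CBC on day 28 of each cycle (8.2) |
| Atrial fibrillation | Periodic clinical monitoring; ECG if symptoms | ECG on day 28 of each cycle (8.5) |
| TLS | Close monitoring and precautions in patients at risk | Chemistry on day 28 of each cycle (8.3), without uric acid |

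The first two warnings have procedures that fit them. TLS has the strongest monitoring language of the three and the same four-weekly interval.

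**2. Day count, current plan**

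Inputs: baseline chemistry 0 to 7 days before day 1 (7.2); first on-treatment chemistry on day 28 ± 2, that is day 26 to day 30 (8.3, note f).

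- First dose to first on-treatment chemistry: 26 − 1 = 25 days, to 30 − 1 = 29 days.
- Shortest gap from baseline: 0 + 25 = 25 days.
- Longest gap from baseline: 7 + 29 = 36 days.
- Scheduled chemistries inside that gap: 0.
- Scheduled uric acid measurements in the whole study: 0.

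**3. Day count with chemistry added at the day 1 24-hour draw and the day 8 4-hour draw**

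- Baseline to day 1, 24 h: at most 7 + 1 = 8 days.
- Day 1, 24 h, to day 8, 4 h: about 6 days.
- Day 8 to day 26–30: 26 − 8 = 18 days, to 30 − 8 = 22 days.

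The longest interval falls from 36 to 22 days. The first on-treatment chemistry moves from 25–29 days to about 24 hours after the first dose.

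**4. Tubes already planned (Appendix C)**

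- Pre-dose: 2 green + 1 yellow = 3.
- Each cycle: day 1 = 1 (4 h) + 3 (24 h) = 4; day 8 = 1 (4 h) + 2 (24 h) = 3; day 28 = 3; total 10.
- Whole study: 3 + 3 × 10 = 33 per patient.
- Cycle 1, after the first dose and before day 28: four draws, 1 + 3 + 1 + 2 = 7 tubes, none for chemistry.
- Two added tubes: 2/33 ≈ 6% more per patient, or 2 × 12 = 24 tubes for the full enrolment of 12.

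**5. Analytes**

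A six-analyte set is assumed for TLS monitoring: potassium, phosphorus, calcium, creatinine, LDH and uric acid. The documents do not define one. Five of the six are already in the protocol's panel; uric acid is missing.

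**The case against.** The strongest reply is that section 4.9 is drug information, not a scheduling commitment. It names no test or time and directs precautions to patients at risk, which is a judgement about the individual. Where it does give a frequency, for CBCs, the schedule meets it. Cycle 1 uses the standard 420 mg dose from commercial supply, so the trial adds sampling and not exposure in that cycle. Prophylaxis is permitted, adverse events are evaluated throughout, and nothing bars unscheduled chemistry. Baseline CBC, LDH, beta-2-microglobulin and examination inform a judgement of tumor burden, and CT is allowed as standard of care. Section 4.9 gives percentages for other risks but none for TLS. The proposed time points follow existing draws and not a known onset time, and they still leave 18 to 22 days without chemistry after day 8.

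Much of this stands. The size of the risk cannot be shown from the documents. An ALC of at least 20 × 10⁹/l does not by itself place every patient at TLS risk, because no threshold is set. The remedy shortens the gap without closing it.

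None of it supplies an early scheduled chemistry or a uric acid result. Leaving monitoring to the clinician could be defended if the protocol said so. It instead sets a specific calendar that contains no early test. Because baseline CT is not required, non-palpable nodal disease may also be unknown when the investigator judges who is at risk.

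**Conclusion.** The concern holds. The schedule has no chemistry between baseline and day 28 (± 2) of cycle 1, a gap of 25 to 36 days, and no uric acid at any point, although section 4.9 asks for close monitoring of patients at risk of TLS. Asymptomatic early TLS could be missed or found late by scheduled tests.

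The conclusion is limited to asymptomatic cases and scheduled tests, and assumes that sites order nothing beyond the calendar. No count of affected patients is offered, because the documents give neither a rate nor a time of onset. Confidence that the change is warranted is medium for that reason, while the schedule facts themselves are clear. The change should be made: the safety gain is specific and the cost is small.

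**What to change.** - Add uric acid to the analyte lists in sections 7.2 and 8.3 and in Study Calendar note a.
- In cycle 1 only, send one chemistry tube (potassium, phosphorus, calcium, creatinine, LDH, uric acid) with the existing day 1 24-hour draw and one with the existing day 8 draw, preferably at 4 hours as the earlier of the two.
- State that the investigator reviews these results when they return.

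Applying this to all patients avoids having to define a TLS risk cut-off, which the protocol lacks. CBC timing and treatment rules need no change.

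The cost is two routine tubes per patient (a few ml of blood), one extra analyte, minor laboratory expense and a calendar edit by amendment. No visit or venipuncture is added.

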9 ASSESSMENT OF RESPONSE

There will be no formal response assessment due to the short duration of ibrutinib treatment in this study. For reference, IWCLL criteria² for response, stable and progressive disease are provided in Appendix A. As noted above, lymphocytosis alone does not represent disease progression in the context of ibrutinib therapy.³⁷

10 CRITERIA FOR REMOVAL FROM THE STUDY

- 10.1 Patients with clinically significant progressive disease.
- 10.2 Poor compliance with study treatments or protocol-mandated study procedures.
- 10.3 Unacceptable severe (grade 3-4) toxicity despite dose optimization and optimal management of toxicity.
- 10.4 Patient request.
- 10.5 Lack of appreciable benefit in the presence of better therapeutic options in the opinion of the investigator.

11 STATISTICAL CONSIDERATIONS

Ibrutinib is an inhibitor of Bruton's tyrosine kinase (BTK). The FDA has approved it for relapsed patients with CLL and frontline patients with del17p. Its standard dose is 420 mg/day (three 140-mg capsules). The primary objective of this pilot study is to determine the effects of different daily doses of ibrutinib (420 mg, 280 mg, 140 mg) on free drug levels in plasma, BTK occupancy by ibrutinib, BTK mRNA, BTK phospho- and total protein levels and NF- κ B activity. In total, 12 patients will be enrolled in this study. All patients will receive ibrutinib orally daily for 3 cycles. Each cycle will be 28 days long. In the first cycle, the daily dose of ibrutinib will be 420 mg (3 capsules), in the second cycle, 280 mg (2 capsules) and in the third cycle, 140 mg (1 capsule). That is, each patient will go through the three cycles with decreasing dose levels as described above. The half-life of ibrutinib is 4 to 6 hours and the drug does not accumulate after repeated oral dosing. Therefore, the influence of a previous cycle on the subsequent cycle is minimal.

Among the above pharmacokinetic and pharmacodynamic (PK/PD) parameters, a key factor is BTK occupancy. A dose level with BTK occupancy by ibrutinib $\geq 95\%$ (alternative hypothesis, H1) is regarded as sufficient, and that with an occupancy rate $< 85\%$ (null hypothesis, H0) is insufficient. Using a t-test to test H0 vs. H1, when the standard deviation of BTK occupancy rate (used as a continuous variable) is 0.10, a sample size of 10 to 12 patients can provide 80-88% power, at 2-sided significance level 0.05. This t-test will be conducted for each dose level. The data set described below shows that the standard deviation of BTK occupancy rate is about 5% when its mean is higher than 85%. As such, a sample size of 8 can provide 95% power at significance level 0.01. Therefore, even considering multiple testing adjusted by the Bonferroni method, and sample size reduction due to various reasons, this trial will still have sufficient power. An ideal dose level is sufficiently high to provide a high ($\geq 95\%$) BTK occupancy level by ibrutinib, but not higher, so that there is not much “left over drug” in plasma to cause toxicities, i.e, a low free drug level in plasma is desirable.

Previous clinical experience has shown that lower than standard doses of Ibrutinib have similar efficacy and lower toxicities. In a phase I study of ibrutinib in a different population of patients (with relapsed or refractory B-cell malignancies), BTK occupancy $\geq 95\%$ was achieved 4 hours post-dose in all patients receiving 2.5 mg/kg/day,⁶⁰ which equals 175 mg/day for patients weighing 70 kg. In total, 56 patients were enrolled onto this study with 7 dose levels, and 6 to 9 patients at each dose level, to provide data on means (SDs) of the concentration of ibrutinib over time, areas under the curves (AUCs) of the receiver operating characteristics (ROCs), BTK occupancy (in %) for different dose levels over time, and other PK/PD parameters. For the 7 dose levels, the mean AUCs over 0-24 hours range roughly from 100 to 1500 ng x h/mL, with their SDs ranging roughly from 20 to 400 ng x h/mL, and higher dose levels had larger mean AUCs and larger SDs. For the highest dose level, the mean (SD) concentrations of ibrutinib were roughly 20 (5), 100 (35), 135 (45), 55 (15) ng/mL at 1, 2, 3, and 4 hours after taking the drug. These data show that the sample sizes of 6 to 9 patients at each dose level are sufficient to provide reasonably accurate estimates for these PK/PD parameters. This pilot study will enroll up to 12 patients, but have each patient receive all the three proposed dose levels, one at a time, as described above.

We will also observe the effects of different daily doses of ibrutinib (420 mg, 280 mg, 140 mg) on clinical parameters in patients with CLL in terms of efficacy and safety. We will measure the absolute lymphocyte count (ALC), hemoglobin and platelet levels, CLL-related symptoms, and palpable lymphadenopathy and/or hepatosplenomegaly on day 28 of each cycle of treatment. We will characterize the safety and tolerability of ibrutinib throughout the study. Descriptive statistics will be used. Continuous variables e.g., clinical characteristics such as CBC parameters, and laboratory correlates such as plasma drug levels, BTK occupancy, mRNA and protein levels, and NF- κ B activity levels, will be summarized using the mean (SD) and/or median (range). Frequency tables will be used to summarize categorical variables.

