2.2 Ibrutinib mechanism of action and preclinical data in CLL

B-cell receptor (BCR) signaling plays a key role in CLL pathogenesis, and BTK has a critical role in BCR signaling in both normal and malignant B-cells.^{7,8} BTK is important for antigen-induced BCR activation in both normal, mature B-cells and in CLL and mediates survival and proliferation via amplification of downstream effector pathways, e.g., phosphatidylinositol 3-kinase/Akt (PI3K/Akt), mitogen activated protein kinase/extracellular signal-regulated kinase (MAPK/ERK) and nuclear factor kappa B (NF- κ B).^{7,8} Additionally, autonomous BCR signaling has also been described in CLL, which is not, however, associated with activating mutations in any of the BCR components.⁸

Ibrutinib inactivates BTK through irreversible, covalent bonding to the Cys481 residue in the adenosine triphosphate (ATP)-binding domain of BTK.⁹ BTK has been shown to be critical for the development and expansion of CLL and an important target of ibrutinib.¹⁰ Indeed, BTK point mutations (C481S) that convert ibrutinib to a reversible inhibitor, as well as activating mutations in phospholipase C gamma 2 (PLC γ 2), located immediately downstream of BTK, have been implicated in the pathogenesis of acquired resistance to ibrutinib in CLL.¹¹ The success of the more selective BTK inhibitor, acalabrutinib, in heavily pretreated

patients with CLL, further testifies to the relevance of BTK as a major therapeutic target in this disease.¹²

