Data from our laboratory further extends these observations. We found that total BTK protein was decreased in primary circulating CLL cells obtained from patients undergoing ibrutinib therapy ([name], unpublished data). Collectively, these observations suggest that total BTK protein levels decline with ibrutinib treatment. Finally, BTK-dependent NF- κ B activation, resulting from both BCR^{63,64} and toll-like receptor (TLR)⁶⁵ activation, is inhibited by ibrutinib, and NF- κ B regulates the level of BTK protein through control of transcription,⁶⁶ providing yet another mechanism by which ibrutinib therapy may lead to reduced levels of BTK protein. Because ibrutinib is an irreversible inhibitor and one molecule of drug is needed for stoichiometrically inhibiting the enzyme, a lower level of protein would mean a lower concentration of ibrutinib required for BTK inhibition. In the presence of higher levels of circulating ibrutinib than are required to establish full BTK occupancy, these phenomena would be expected to increase the likelihood of off-target binding of the drug, potentially leading to AEs.

Impact on drug cost

Finally, the cost of ibrutinib therapy (average wholesale US price \$11,002 per month), especially in the likely future scenario of an expanded frontline indication, is prohibitive. Costs of indefinite therapy with tyrosine kinase inhibitors (TKIs) have already been noted to be unsustainable in the context of chronic myeloid leukemia.⁶⁷ In the current paradigm,

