6.2 Treatment plan

Patients will receive ibrutinib orally daily for 3 cycles. Cycles will be 28 days long. Ibrutinib will be administered continuously, at approximately the same time each day, without regard to food. In the first cycle, the daily dose of ibrutinib will be 420 mg (3 capsules), in the second cycle, 280 mg (2 capsules) and in the third cycle, 140 mg (1 capsule). Patients will swallow the ibrutinib capsules whole with water without opening, breaking or chewing them.

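### Section 11 infers minimal influence between cycles from the plasma half-life; this holds for plasma ibrutinib but not for BTK occupancy and the other BTK endpoints, where dose cannot be separated from time on therapy

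*Combined protocol and SAP*

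**What the plan says.** Section 11 describes a single fixed sequence in which "each patient will go through the three cycles with decreasing dose levels as described above", that is 420, 280 and then 140 mg for 28 days each. Section 6.2 leaves no gap between cycles: "Ibrutinib will be administered continuously, at approximately the same time each day, without regard to food". From the 4 to 6 hour half-life and the lack of accumulation, Section 11 then concludes: "Therefore, the influence of a previous cycle on the subsequent cycle is minimal". No endpoint is excepted.

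The next paragraph singles out BTK occupancy as a key factor and sets up the only hypothesis test, below 85% (insufficient) against at least 95% (sufficient): "This t-test will be conducted for each dose level". It does not say which draw is tested. Appendix C lists five post-dose draws per cycle: day 1 at 4 and 24 hours, day 8 at 4 and 24 hours, and day 28 at 24 hours. Study Calendar footnote c adds that time zero of cycles 2 and 3 is the previous cycle's day-28 24-hour sample.

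The background sections describe the target differently from plasma. Section 2.2: "Ibrutinib inactivates BTK through irreversible, covalent bonding to the Cys481 residue". Section 3: "Collectively, these observations suggest that total BTK protein levels decline with ibrutinib treatment", and, because binding is irreversible and one molecule of drug is needed per enzyme molecule, "a lower level of protein would mean a lower concentration of ibrutinib required for BTK inhibition".

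**The concern.** Plasma half-life governs how long the drug stays in plasma. It does not govern how long irreversibly bound enzyme stays bound, nor how long a treatment-induced fall in BTK lasts. For the BTK endpoints the stated premise therefore does not lead to the stated conclusion, and Section 3 points the other way.

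The design offers nothing to offset this: no washout, no varied order and no period analysis. Each dose level occurs at one time on therapy only. A favourable occupancy result at 140 mg could reflect the dose, the preceding eight weeks of ibrutinib, or both. Section 11 would nevertheless call the dose level sufficient, without saying that the finding applies after step-down. If the t-test used a day-1 draw of cycle 2 or 3, much of what it measured could belong to the previous dose.

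**Working it through.** **1. The plan's own figure.** Inputs from Section 11: null mean 0.85, alternative 0.95, two-sided one-sample t-test (noncentral t). At SD 0.10 and alpha 0.05, power is 80.3% for n = 10 and 88.3% for n = 12, which agrees with "a sample size of 10 to 12 patients can provide 80-88% power". At SD 0.05, alpha 0.01 and n = 8 it is 95.1%, against the stated 95%. The power arithmetic is sound.

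**2. Plasma.** The fraction left 24 hours after a dose is 0.5^(24/half-life): 0.5^(24/4) = 1.6% and 0.5^(24/6) = 6.25%. At 48 hours it is below 0.4%. For plasma ibrutinib the sentence holds.

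**3. Direct carry-over of bound BTK.** The documents give no BTK turnover rate and no fraction bound per dose, so everything in this step is assumed:

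- BTK half-life h = 12 to 168 h, so the share of enzyme surviving each day is s = 0.5^(24/h)
- a fraction f = 0.30 to 0.85 of free BTK bound by each 140 mg dose
- occupancy of 95% just before the first 140 mg dose, against 0% in an untreated patient

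The starting gap in occupancy is 0.95. Each dose multiplies it by (1 − f) and each day by s. Just after dose n (taken to represent the 4-hour draw) the gap is 0.95 × (1 − f)^n × s^(n − 1). At 24 hours it is multiplied by s once more.

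| Time in cycle | Smallest gap | Largest gap |
|---|---|---|
| Day 1, 4 h | 0.95 × 0.15 = 14 points | 0.95 × 0.70 = 67 points |
| Day 1, 24 h | 0.95 × 0.15 × 0.25 = 4 points | 0.95 × 0.70 × 0.906 = 60 points |
| Day 8, 4 h | about 0 | 0.95 × 0.70^8 × 0.5 = 2.7 points |
| Day 8, 24 h | about 0 | 2.7 × 0.906 = 2.5 points |
| Day 28, 24 h | 0.0 | 0.0 |

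With f between 0.50 and 0.85, the day-8 gap is at most 0.2 points.

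**4. Fall in total BTK.** Section 3 gives no size, time course or dose relation. As an illustration only, take h = 24 h and f = 0.70, and let a fall of BTK to a fraction B of its level raise the bound fraction to 1 − (1 − 0.70)^(1/B). Steady-state occupancy just after a dose is f/(1 − (1 − f) × 0.5):

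- no fall: 0.70/0.85 = 82%
- 25% fall: f = 0.799, giving 89%
- 50% fall: f = 0.91, giving 95%

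The 24-hour values are half of these: 41%, 44% and 48%. A fall that lasts would therefore still act on day 28, where direct carry-over is gone.

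**5. Why 140 mg in particular.** At Section 11's 70 kg, 280 mg is 280/70 = 4.0 mg/kg. That is inside the 2.5 to 12.5 mg/kg range in which Section 3 reports more than 95% occupancy in all cohorts. 140 mg is 140/70 = 2.0 mg/kg, below that range. On exposure, Section 3 reports complete or near-complete occupancy above an AUC of 160 ng·h/mL, and Section 4.4 gives 680 ± 517 at 420 mg. Assuming dose proportionality, 140 mg gives 680/3 = 227 with SD 517/3 = 172. The mean is above the threshold, but the spread is wide enough for many patients to fall below it.

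**6. What a small lift would do to the test.** Suppose true occupancy without prior treatment were 85% and prior treatment added 2 points (both assumed). With n = 12 and two-sided alpha 0.05, the chance of declaring the dose above 85% rises from 2.5% to 24% at SD 0.05, or to 9% at SD 0.10.

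**The case against.** The strongest reply is that step-down is the trial's own idea. Section 3 argues that less drug is needed once BTK has fallen, Section 11 states the descending order openly, and this is a 12-patient pilot. That stands: the sequence is not an error. But if step-down is the strategy under study, a sentence that rules out influence between cycles contradicts it, and the conclusions need the step-down condition.

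A second reply is that direct carry-over is confined to the first days of a cycle, and that no section says the t-test uses those days. This largely stands, and it limits the size of the problem. Because the draw is unnamed, though, the day-1 draws are not excluded either.

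Third, the evidence for a BTK decline is murine work and unpublished laboratory data, and it links the decline to ibrutinib treatment, not to higher doses. A patient on 140 mg from the start might show the same fall. This also stands. A reader might infer that prior higher dosing specifically inflates the 140 mg result; the documents support only confounding with time on therapy.

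Two other inferences go too far. One is that 140 mg is insufficient: it lies below the reported mg/kg range, but the documents give no occupancy figure there, and the scaled mean AUC is above the threshold. The other is that the power statement is wrong: it reproduces.

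**Conclusion.** The concern holds as a fault of scope. The half-life argument supports minimal influence between cycles for plasma ibrutinib only. For BTK occupancy, BTK mRNA and protein, downstream signalling and NF-κB it is unsupported, and Sections 2.2 and 3 give reasons to doubt it. With one descending sequence, no analysis can separate dose from time on therapy. Occupancy at 280 mg and especially 140 mg may look better than it would without prior treatment.

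The wording defect is certain; the size of any bias is not known. Under the assumed turnover model, direct carry-over matters at the cycle 2 and 3 day-1 draws, is at most about 3 points on day 8 and is nil on day 28. A treatment-related BTK decline could affect later draws, but its size, time course and relation to dose are unknown. The point should be fixed, because it changes what the trial can conclude about the lower doses.

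**What to change.** In Section 11:

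1. Limit the minimal-influence sentence to plasma ibrutinib, and state that for the other endpoints dose is confounded with time on therapy.
2. Name a late-cycle draw for the per-dose occupancy t-test. The day-28 24-hour draw is the cleanest. Day 8 is also nearly free of direct carry-over, and its 4-hour draw matches the timing of the cited phase I occupancy figure. Do not use the cycle 2 and 3 day-1 draws for this test, and treat time zero of those cycles as belonging to the previous dose.
3. Word conclusions on 280 and 140 mg as applying after step-down from 4 and 8 weeks of prior ibrutinib, and do not attribute between-cycle differences in clinical or safety data to dose alone.

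This needs only wording and one named sample, all from data already planned: no new patients, draws or models. The price is a narrower claim. Naming a late draw limits direct carry-over but does not remove the confounding with time on therapy.
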